#### 12.1.4 Handling of Missing Values and of Values outside the Detection Limits

In general, missing data will not be imputed.

For questionnaire data total scores and domain or subscale scores a certain degree of imputation may occur by averaging across individual item scores. Further details will be provided in the SAP.

For biological measurements, values below the lower limit of quantification (LLOQ) will be imputed using  $0.5 \times$  lower limit of quantification. For values above the upper limit of quantification (ULOQ), i.e., preceded by a “>”, for example “>xx,” the numerical xx will be used for calculation and reporting in summary tables. The number and percent of values below LLOQ or above ULOQ will be presented in each summary table.

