### 12.6.3 Safety Endpoints

In general, all safety data will be listed and tabulated as described in section 12.1.3.

AE data will serve for the primary assessment of safety. Other safety variables monitored in this study include: incidence and frequency of P3P product events including malfunction/misuse; respiratory symptoms (cough assessment VAS and Likert scales); vital signs; spirometry; ECG data; clinical chemistry, hematology, and urine analysis safety panel; physical examination; concomitant medications.

The number and percentage of subjects with AEs, SAEs, and product events will be tabulated by system organ class and preferred term. Summaries will also be presented for AEs leading to discontinuation, AEs leading to death, AEs by relatedness to product exposure (with and without laboratory related AEs), AEs by severity, and laboratory AEs. Tabulations will be performed for both the number of subjects experiencing an event and the number of events.

Summary tables showing actual values and change from baseline of clinical findings will be provided for spirometry, ECGs, vital signs, and laboratory parameter. Descriptive statistics will be summarized by product variant and change from baseline will be presented for laboratory parameters, ECG, respiratory symptoms, and vital signs. Shift tables will be provided for selected laboratory, spirometry, and ECG data.

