5.2 Secondary Objectives and Endpoints

1. To evaluate the pharmacodynamic effects (subjective effects and related behavioral assessments) of the two P3P variants.

Endpoints:

- Visual Analogue Scale (VAS)-craving assessment in parallel with PK assessment on Day 1 and Day 30;
- Sensory Questionnaire on Day 1 and Day 30;
- ABOUT™-Product Experience Questionnaire on Day 1 and Day 30.

2. To assess product acceptance and puffing/inhalation behavior of both P3P variants

Endpoints:

- Product acceptance questionnaire on Day 1 and Day 30;
- Puffing/inhalation behavior question:
 - Evaluated by site staff on Day 1 and Day 30
 - Answered by subject on Day 2, Day 7, Day 15, Day 22 and Day 29.

3. To assess nicotine/tobacco product use.

Endpoints:

- Number of P3P, cigarettes, e-cigarettes or/and other nicotine/tobacco product use from Day 1 to Day 30;
- Change in the number of cigarettes used throughout the study as compared to the reported number at Screening.

4. To assess safety and tolerability during the study.

Endpoints:

- Incidence of adverse events (AEs), serious adverse events (SAEs);
- Frequency of adverse events (AEs), serious adverse events (SAEs);

- Incidence of P3P product events including malfunction/misuse;
- Frequency of P3P product events including malfunction/misuse;
- Physical examination changes from baseline;
- Cough assessment changes from baseline (VAS and three Likert scales);
- Electrocardiogram (ECG) changes from baseline (heart rate, PR, QRS, QT, QTcB, QTcF intervals);
- Vital signs changes from baseline (systolic and diastolic blood pressure, pulse rate and respiratory rate);
- Spirometry changes from baseline (FEV1, FEV1 % predicted, FVC, FVC % predicted, FEF 25, FEF 25 % predicted, FEF 75, FEF75 % predicted, FEF 25-75, FEF 25-75 % predicted, FEV1/FVC);
- Changes from baseline in clinical chemistry, hematology, and urinalysis safety panel;
- Concomitant medications.

5. To assess the exposure to harmful and potentially harmful constituents (PHHCs) in spot urine expressed as concentration adjusted for creatinine from Day -1 to Day 30.

Endpoints:

- Biomarker of exposure (BoExp) to nicotine: Nicotine equivalents (NEQ);
- BoExp to NNK: 4-(Methylnitrosamino)-1-(3-pyridyl)-1-butanol (total NNAL);
- BoExp to Acrylonitrile: 2-cyanoethylmercapturic acid (CEMA).

6. To assess tobacco and nicotine containing product dependence at Day -1 and at Day 30.

Endpoint:

- ABOUTTM-Dependence Questionnaire.

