7.8.2 Cough Assessment

At V2-V6, subjects will be asked if they have experienced a regular need to cough, e.g., whether they have coughed several times in the previous 24 hours prior to assessment. If the answer is 'yes', they will be asked to complete a cough assessment questionnaire (which includes a VAS and three Likert scales).

The VAS will assess how bothersome cough is to the subject, on a 10 cm scale ranging from 'not bothering me at all' to 'extremely bothersome'.

Subjects will also be asked to assess the intensity and frequency of cough and the amount of sputum production on Likert scales as presented in Table 6: Cough Assessment Likert Scales.

Table 6: Cough Assessment Likert Scales

Question	Likert Scale
1 The intensity of cough	1 = very mild 2 = mild 3 = moderate 4 = severe 5 = very severe
2 The frequency of cough	1 = rarely 2 = sometimes 3 = fairly often 4 = often 5 = almost always
3 The amount of sputum production	0 = no sputum 1 = a moderate amount of sputum; 2 = a larger amount of sputum; 3 = a very large amount of sputum.

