12.1.4 Definitions of Baseline for Statistical Data Analysis

Baseline values for pharmacodynamic parameters (VAS Craving, Sensory Questionnaire, ABOUT™-Product experience), Product Acceptance, ABOUT™-Dependence, and Puffing/Inhalation behavior questions are defined in section 7.1, 7.2.1, 7.2.2, 7.2.3, 7.3.1, 7.5.1 and 7.3.2 respectively.

Baseline values of BoExp will be defined as the value measured on V2 (Day -1) when spot urine should be collected prior to product test. Baseline for CYP2A6 will be defined as the value determined on Day 1, see section 7.6.

For safety parameters the last assessment prior to product test at Day -1 will be considered as baseline.

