12.5.9.5.6 Assessment of Cough

Cough questionnaire is assessed at Day -1, 2, 7, 15, 22, and 29. The number and % of subjects reporting a cough will be summarized by P3P variant. The responses to the individual items, including the VAS evaluating the level of cough bother and 3 Likert scales measuring the intensity, the frequency of cough and the amount of sputum production will be listed and summarized on each day by P3P variant, for all subjects who filled in the questionnaire.

The data will be presented in the below outputs:

TFL number	Title
TABLES	
15.2.32.1	Number and Percentage of Subjects with Cough – Safety Population
15.2.32.2	Summary of VAS Level Cough Bothersome by Timepoint – Safety Population
15.2.32.3	Summary of Intensity, Frequency of Cough and Sputum Production by Timepoint – Safety Population
LISTINGS	
15.1.32.1	Listing of Cough Assessment Results – VAS measurement
15.1.32.2	Listing of Cough Assessment Results - Frequency of Cough and Sputum Production

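### Cough VAS and Likert scores are summarised only among subjects coughing at that visit, so the stated change-from-baseline endpoint leaves out all new and resolved cough

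*SAP*

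**What the plan says.** SAP 5.2 lists among the safety endpoints "Cough assessment changes from baseline (VAS and three Likert scales". Protocol 3.2 has the same item. Protocol 12.6.3 identifies respiratory symptoms with the cough VAS and Likert scales and says that "change from baseline will be presented for laboratory parameters, ECG, respiratory symptoms, and vital signs".

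The scales are conditional. At V2 to V6 each subject is asked about a regular need to cough over the previous 24 hours. "If the answer is 'yes', they will be asked to complete a cough assessment questionnaire" (SAP 7.8.2; Protocol 7.7.6 has the same rule). The VAS is a 10 cm line whose lower end means no bother. Intensity and frequency run from 1 to 5 with no level for absence of cough. Sputum runs from 0 to 3.

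SAP 12.5.9.5.6 plans two things. First, "The number and % of subjects reporting a cough will be summarized by P3P variant". Second, the VAS and Likert items are summarised on each day "for all subjects who filled in the questionnaire". Neither its text nor its output titles (Tables 15.2.32.1 to 15.2.32.3) mention change from baseline or a shift table.

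Other rules that bear on the point:
- SAP 7 defines change as the value at the timepoint minus the subject's own baseline value.
- SAP 12.1.4 sets the baseline: "For safety parameters the last assessment prior to product test at Day -1 will be considered as baseline".
- Protocol 12.1.4 states "In general, missing data will not be imputed". No rule in either document gives a score to a 'no' answer.
- SAP 9, which lists departures from the protocol analysis, does not mention cough.

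**The concern.** The people who contribute a score at a visit are selected by their cough status at that visit, which is itself an outcome after exposure. A subject who starts to cough on P3P has no Day -1 score, and one whose cough clears has no later score. Neither can have a change from baseline. Comparing responder means across visits compares different people.

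This matters because P3P is an inhaled powder, Protocol 2.3.3 lists cough among the effects a user may experience, and tolerability is a stated objective. Adverse event reporting is not a guaranteed backstop. Protocol 7.7 says that symptoms recorded on questionnaires need not also be recorded as AEs, because the questionnaires will be analysed, and leaves the choice to the Investigator. The questionnaire analysis therefore has to stand on its own.

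**Working it through.** The documents give no cough rate, no VAS value and no figure for this endpoint, so there is nothing to reproduce. The arm size of about 30 is from SAP 8. All cough rates and scores below are assumptions chosen for illustration.

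**Who can have a change score.** Change needs a score at Day -1 and at the later visit.

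| Day -1 | Later visit | Change score? |
|---|---|---|
| yes | yes (persistent) | yes |
| no | yes (new) | no, baseline absent |
| yes | no (resolved) | no, later value absent |
| no | no | no, both absent |

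Expected pairs per arm = 30 × baseline cough rate × persistence. At 10% and 25% this is 30 × 0.10 × 0.25 = 0.75. At 40% and 100% it is 30 × 0.40 × 1.00 = 12. So between about 1 and 12 of 30 subjects would carry the endpoint.

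**How the responder mean behaves.** Take 3 coughers at baseline with VAS 5. At a later visit the same 3 are unchanged and 6 new coughers score 2.
- Responder mean: 15/3 = 5.0, then (15 + 12)/9 = 3.0.
- Paired change: 0 (n = 3).
- All-subject mean with 'no' as 0: 15/30 = 0.5, then 27/30 = 0.9.
- Percent with cough: 3/30, then 9/30.

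**When the direction reverses.** With m persistent coughers fixed at a and k new coughers at v, the responder mean changes by k(v − a)/(m + k), and the all-subject mean changes by k·v/30. The first is negative only if v < a; the second is always positive for v > 0. For m = 6, a = 5:

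| k | v | Responder mean change | All-subject mean change |
|---|---|---|---|
| 3 | 4 | −0.33 | +0.4 |
| 3 | 1 | −1.33 | +0.1 |
| 12 | 4 | −0.67 | +1.6 |
| 12 | 1 | −2.67 | +0.4 |
| 12 | 5 | 0.00 | +2.0 |
| 12 | 6 | +0.67 | +2.4 |

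Over k = 3, 6 or 12 and v = 1 to 4, the responder mean falls by 0.33 to 2.67 while the all-subject mean rises by 0.1 to 1.6.

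**Improvement can also look like worsening.** Six coughers stay at 6, and six at 2 resolve. Responder mean: (36 + 12)/12 = 4.0, then 36/6 = 6.0. All-subject mean: 48/30 = 1.6, then 36/30 = 1.2. Paired change: 0 (n = 6).

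**The omission set beside the other safety sections.** The SAP text names change from baseline for laboratory data (12.5.9.4), vital signs (12.5.9.5.3), spirometry (12.5.9.5.4) and ECG (12.5.9.5.5). The cough section does not.

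**Assessment day.** SAP 12.5.9.5.6 lists Days -1, 2, 7, 15, 22 and 29. Protocol Table 7 schedules the cough assessment on Day 1, and Protocol Table 8 lists none on Day 2.

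**The case against.** The same paragraph of the SAP tabulates the number and percentage coughing, by variant, in the Safety population. In the example that table would read 3/30 and then 9/30, so the worsening is visible. SAP 12.1.3 also requires n and the number missing, and individual responses are listed. Incidence plus severity among those coughing is a legitimate two-part description. This stands, and a reader should not infer that a rise in cough would be hidden. What the table lacks is the split into new, resolved and persistent cough, and it carries no severity.

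A reader might also infer that the SAP has dropped change from baseline. The documents do not support that. SAP 12.1.3 adds it to summaries when applicable, Protocol 12.6.3 still promises it, and the detailed outputs sit in a separate shell document (SAP 3) that is not available here. The cough section is silent; it does not rule change out. But a change score added under the general rule would still cover only subjects coughing at both visits.

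Scoring every 'no' as zero on all four scales goes too far. The question concerns regular cough, so a 'no' is compatible with an occasional cough, and it says nothing definite about sputum. Intensity and frequency have no zero level. A zero-filled mean can mislead too. Let four baseline coughers score 3, 3, 6 and 6, and let the first two later reach 9 while the others resolve. The all-subject mean is 18/30 = 0.6 both times. The responder mean goes from 4.5 to 9.0, and the paired change is +6 (n = 2). The all-subject mean should therefore not be shown alone.

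Finally, the study is descriptive, AEs are the primary safety assessment, and cough is not among the topline outputs in SAP 13.2. That limits the stakes.

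**Conclusion.** The point holds as a cheap improvement to a secondary, descriptive safety endpoint. As written, the plan cannot give a change in cough severity for any subject whose cough is new or has resolved, and it does not say how a 'no' answer enters the scores. This follows from the documents and needs no assumption about the data.

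The size does rest on assumptions. The shift from 5.0 to 3.0 against 0.5 to 0.9, and the range of about 1 to 12 evaluable pairs per arm, use invented rates and scores. A reader might infer that the responder mean will move the wrong way. It does so only when new cough is milder than the existing average, or when the milder coughs are the ones that resolve. New cough of equal severity leaves it unchanged, and more severe new cough moves it in the right direction.

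**What to change.** In SAP 12.5.9.5.6, for the Safety population by variant and visit:

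1. Add a shift table from Day -1 for the yes/no cough question: none, new, resolved, persistent.
2. Summarise cough VAS and its change from Day -1 in all subjects who answered the yes/no question, counting 'no' as 0. Keep a missed assessment as missing. Zero is reasonable here because it matches the lower anchor of the VAS.
3. Tabulate intensity, frequency and sputum with 'no regular cough' as a separate lowest category, without assigning it a numeric score.
4. Keep the responders-only summary beside these, labelled as conditional on coughing.

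Also reconcile the assessment day between SAP 12.5.9.5.6 and Protocol Tables 7 and 8.

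Cost: SAP wording, one derivation and a few extra outputs, all from data already collected. Downside: VAS 0 is an approximation for a subject with an occasional cough who answers 'no'.

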13 ANALYSIS AND REPORTING

13.1 Interim Analysis

No interim analysis is planned on this study.

13.2 Topline Results

Topline results, composed of key statistics and study results listings, will be made available to PMPSA following database lock and prior to completion of the complete set of TFLs. The following tables, figures, and listings will be made available following database lock:

TFL no.	Title
TABLES	
15.2.4.1	Summary of Demographics and Other Baseline Characteristics – Safety Population
15.2.8.3	Descriptive Statistics of Product Exposure by Period - Safety Population
15.2.9.1	Descriptive Statistics of Background-Corrected and Uncorrected Pharmacokinetic Parameters of Nicotine (AUC _(0-4h) and C _{max}) at Day 1 and Day 30 – PK Population
15.2.9.2	Analysis of Background-Corrected and Uncorrected Pharmacokinetic Parameters of Nicotine (AUC _(0-4h) and C _{max}) at Day 30 and at Day 30 relative to Day 1 – PK Population
15.2.12.1	Descriptive Statistics of Background-Corrected Plasma Nicotine Concentration at Day 1 and Day 30 by Timepoint– PK Population
15.2.12.2	Descriptive Statistics of Uncorrected Plasma Nicotine Concentration at Day 1 and Day 30 by Timepoint– PK Population
15.2.13.2	Analysis of AUC _{VAS Craving (0-4h)} at Day 1 and Day 30 and Change from Day 1 at Day 30 – Randomized Population
15.2.18.3	Descriptive Statistics of Change from Baseline in Average Cigarettes smoked /day - By Period– Safety Population
15.2.23.1	Summary of Adverse Events – Safety Population
15.2.23.2	Summary of Adverse Events by System Organ Class and Preferred Term – Safety Population
15.2.25.1	Summary of P3P Product events by Subject - Safety Population
15.2.26.2	Summary of Clinical Chemistry Parameters - Safety Population
15.2.26.7	Summary of Hematology Parameters - Safety Population
15.2.26.12	Summary of Urinalysis Parameters - Safety Population
15.2.30.1	Descriptive Statistics of Spirometry Results- Safety Population
FIGURES	
15.3.2.1	Background-Corrected Plasma Nicotine Concentration-Time Profiles at Day 1 and Day 30- Linear-- PK Population
15.3.2.2	Uncorrected Plasma Nicotine Concentration-Time Profiles at Day 1 and Day 30–Linear- PK Population
15.3.3.1	VAS Craving Score Profiles By Timepoint at Day 1 and Day 30 – Randomized Population
LISTINGS	
15.1.23.1	Listing of Exposure Emergent Adverse Events
15.1.23.4	Listing of AEs leading to study discontinuation

13.3 Final Analyses

Final analyses for this study will be performed only after database lock. A pre-analysis data review meeting will be held prior to database lock and completion of the final analyses. In addition, no database may be locked, randomization code unblinded, or analyses completed until the final version of this SAP has been approved.

Any post-hoc, additional exploratory analyses completed to support planned study analyses, which were not identified in this SAP, will be documented and reported as applicable. Any results from these unplanned analyses will also be clearly identified in the text of the RSR.

The list of all tables, figures and listings to be presented are included in the relevant sections of the SAP.

14 DATA PRESENTATION

A separate TFL style guide document will be provided.

16 APPENDICES

Appendix A – Schedule of Events

Philip Morris Products S.A.
Protocol P3P-SE-02-RU

Statistical Analysis Plan

Page 72 of 76

	Screening	Admission	Product use period (up to 15 products/day)					Discharge	Early termination	Safety Follow-Up
Visit	1	2		3	4	5	6			
Study day	-22 to -2	-1	1	2	7 ±2d	15 ±2d	22 ±2d	29 ±2d	30 ±2d	+14 days
Willing to continue to use P3P for 1 Month (confirmation after product test)		•								
Randomization		•								
B: CYP2A6 activity ^h			•						•	
Overnight nicotine wash-out period ⁱ		•						•		
P3P single product use for PK assessment ^j			•						•	
Weighing of P3P ^k			•						•	
Collection of used and unused P3P ^l					•	•	•	•	•	
On-site product use (up to 15 P3P)			•	•						
P3P resupply				•	•	•	•			
B: nicotine in plasma ^m			•						•	
U: BoExp ⁿ		•			•	•	•	•		
B/U: Biobanking			•						•	

Philip Morris Products S.A.
Protocol P3P-SE-02-RU

Statistical Analysis Plan

Page 74 of 76

Abbreviations: ABOUT = Assessment of Behavioral Outcomes related to Tobacco and nicotine products; AE = Adverse event; B = Blood sample; BMI = Body mass index; BoExp = Biomarkers of Exposure; ECG = Electrocardiogram; PK = Pharmacokinetics; SAE = Serious adverse event; U = Urine sample; VAS = Visual analog scale

- a. Prior to enrollment, at Day -1 the following eligibility criteria will be re-checked: Inclusion criteria: smoking status confirmed by urine cotinine, subject is not planning to quit smoking within 2 months, subject is available for the entire study period and is willing to comply with the study procedures. Exclusion criteria: urine pregnancy test (all females), urine drug screen and alcohol breath test. The following eligibility criteria will only be checked at Day -1: Exclusion criteria: subject has received medication which has an impact on CYP2A6 activity within 14 days or within 5 half-lives of the drug prior to Day -1 (whichever is longer)
- b. Pre-study chest X-ray (with anterior-posterior and left lateral views). Available chest computed tomography (CT) or chest magnetic resonance imaging (MRI) results, or radiologist report from an equivalent radiological assessment within 6 months prior to Screening.
- c. Systolic and diastolic blood pressure, pulse rate, and respiratory rate. At V2 (Day -1, Day 1 and Day 2) and V6 (Day 30) vital signs are to be checked prior to any product use and at the end of the day/at discharge.
- d. Subjects with a BMI $< 18.5 \text{ kg/m}^2$ or BMI $\geq 32 \text{ kg/m}^2$ will be excluded. At V2 and V6 weight only will be recorded.
- e. Spirometry with and without bronchodilator performed at Screening. Spirometry without bronchodilator performed at the remaining visits. At Day -1, spirometry will be performed before and after product test. At Day 1 and Day 2 spirometry will be performed before product use and at the end of the daily product use.
- f. Only medication used for treatment of an AE/SAEs
- g. P3P product test using up to 6 P3P products (both P3P-1mg and P3P-2mg) will be conducted at Day -1 after enrollment. A wash-out period from any tobacco/nicotine containing products of at least 4 h prior to product test is needed.
- h. Sample taken in the morning prior to product use.
- i. Starting on the first day of each confinement period, subjects will abstain from tobacco/nicotine containing products for at least 10 h prior to P3P use for PK assessment on the second confinement day.
- j. Use of a single product with puffing depending on the subjects preference (*ad libitum* use) for a duration of up to 15 minutes.
- k. Each P3P used for PK assessment should be weighed prior to product use and within 1h after the end of the use.
- l. On Day 29 collection of unused P3P should occur right before the start of the 10h wash-out period.
- m. A total of 11 blood samples will be taken for PK parameter estimation at Day 1 and Day 30. Three blood samples will be taken prior to the start of product use (T_0) 1 hour \pm 5 minutes, 30 minutes \pm 5 minutes and 5 minutes \pm 2 minutes before T_0 . Thereafter in relation to T_0 , blood will be drawn at the following time points: after 4 minutes \pm 1 minute, after 7 minutes \pm 1 minute, after 10 minutes \pm 1 minute, after 15 minutes \pm 2 minutes, after 30 minutes \pm 2 minutes, after 1 hour \pm 5 minutes, after 2 hours \pm 5 minutes and after 4 hours \pm 5 minutes.
- n. NEQ, total NNAL and CEMA will be analyzed in spot urine and adjusted for creatinine.

Philip Morris Products S.A.

Protocol P3P-SE-02-RU

Statistical Analysis Plan

Draft v 1.0 / 17 July 2019

Confidential

Page 76 of 76

- o. Daily during the exposure period. Use of P3P and any other tobacco and nicotine containing products will be captured in a diary starting from Check-out of Day 1 until Discharge at Day 30.
- p. First assessment to be done 10 ± 2 minutes prior to T_0 . Thereafter, in relation to T_0 , assessment is to be performed at 4 minutes ± 2 minutes, 10 minutes ± 2 minutes, 15 minutes ± 2 minutes, 30 minutes ± 5 minutes, 1 hour, 2 hour and 4 hours ± 10 minutes each.
- q. At the end of Safety FU (end of V6 + 14 days) the site will call all subjects to collect new AEs/SAEs and to follow-up ongoing AEs/SAEs. If the subject is not responding at the initial call, 2 additional attempts on the next consecutive
